4 STUDY DESIGN

4.1 OVERALL DESIGN

This is a single-center, sham-controlled study to investigate the efficacy and safety of RELAY use of a device that enables the delivery of both local anesthetic and neuromodulation (peripheral nerve stimulation) to treat postoperative pain.

Following a training run-in period, the randomized single blind sham-controlled part of the study will commence. The purpose of the training run-in period is to ensure that RELAY can be safely placed next to a target nerve, successfully programmed and induce peripheral nerve block and neuromodulation based on the instructions for use. This will ensure familiarity with the device prior to the randomized portion of the study. The training period will consist of up to 20 participants (~ 5 to 10 catheter lead insertions per anesthesiologist) across at least two different surgical procedures.

It is anticipated that during the training run-in phase, the successful deployment of the RELAY system will be achieved 80% or more of the time. If less than 80% is achieved, the study will not proceed to the randomized portion. A brief study report will be submitted to the FDA prior to initiating the randomized portion.

RELAY deployment success will be defined as a successfully placed catheter/lead as evidenced by sensory changes in the distribution of the target nerve with (1) electrical stimulation eliciting paresthesia and (2) inducing a conduction nerve block with injection of local anesthetic injection leading to either decreased or absent sensation to cold with alcohol swab.

The randomized portion will include 40 participants (with up to 10 additional participants to account for drop-outs) randomized (1:1) to the experimental and sham arms, respectively. A futility analysis will be performed once 20 participants have been randomized and data through post-operative Day 7 are available. The following two criteria must be achieved to move forward: 1) RELAY deployment success in the lead/catheter insertion of $\geq 85\%$ in RELAY participants, and 2) a conditional power (Cp) of $\geq 30\%$ for the primary efficacy endpoint. Of note, a standardized effect size of 0.49 would not meet criteria to continue. There will be no stopping for early efficacy.

4.2 SCIENTIFIC RATIONALE FOR STUDY DESIGN

Postoperative pain remains undertreated with inadequate analgesic options. Opioids have well-known limitations for both individuals and society; single-injection and continuous peripheral nerve blocks provide intense analgesia but are limited in duration to 24-72 hours; and current neuromodulation options—with a duration measured in weeks and not hours—are prohibitively expensive and require an additional procedure. One possible solution is a device currently under investigation to treat postoperative pain. The RELAY system (Gate Science, Moultonborough, New Hampshire) is comprised of a basic catheter-over-needle device to allow administration of a single-injection of local anesthetic via the needle (or catheter) followed by a perineural local anesthetic infusion via the remaining catheter (when desired). Subsequent to the local anesthetic administration, instead of removing the catheter as with all previous continuous peripheral nerve block equipment, electric current may be delivered via the same catheter for up to a total of 28 days. This is potentially revolutionary because it would allow an anesthesiologist to deliver (1) a single-injection peripheral nerve block; (2) a continuous peripheral nerve block; and (3) neuromodulation using a single device that can theoretically be placed in the same amount of time required for a single-injection peripheral nerve block. Instead of providing fewer than 24 hours of postoperative analgesia, up to 28 days of pain control could be delivered without disruption of existing practice patterns. ***The ultimate objective of the proposed research study is to prepare for a large, multicenter clinical trial investigating the use of the RELAY device to provide postoperative analgesia.***

4.3 JUSTIFICATION FOR DOSE

Regarding the local anesthetics, we are using standard volumes and concentration of local anesthetics currently used at our institution. We do not want to change our standard of care for the local anesthetic-based peripheral nerve blocks.

Regarding the electrical stimulation, the pulse generator of the RELAY has a frequency between 1-250 Hz, a pulse duration of 1-200 μ s, and a current of 0.001-10 mA (1-10,000 μ A). If the same pattern holds for the RELAY device as for previously tested peripheral nerve stimulators, we will maximize frequency, minimize pulse duration, and have participants adjust the amplitude, as needed. Participants will use their smartphone to download an app that allows them to increase or decrease the amplitude using a Bluetooth connection with the pulse generator. Participants can only adjust the amplitude and not the other parameters.

4.4 END OF STUDY DEFINITION

The end of the study is defined as completion of the last follow up data collection time point (14 days) of the final enrolled participant.

5 STUDY POPULATION

We will be enrolling adult participants (at least 18 years of age) undergoing a rotator cuff repair, total shoulder arthroplasty, hallux valgus correction, or ankle arthroplasty/arthrodesis. Up to 20 participants will be enrolled to the training run-in period. An additional 40 participants are anticipated for the randomized portion of this study. However, to account for dropouts, we are requesting an additional 10 participants. This will total up to 70 participants overall.

5.1 INCLUSION CRITERIA

1. Adult participants of at least 18 years of age
2. Undergoing a rotator cuff repair, total shoulder arthroplasty, hallux valgus correction or ankle arthroplasty/arthrodesis
3. Planned single-injection peripheral nerve block(s)
4. An Android or Apple smartphone able to download the Gate Keeper controller app

5.2 EXCLUSION CRITERIA

1. Chronic opioid or tramadol use (daily within prior 2 weeks and duration > 4 weeks)
2. Neuro-muscular deficit of the surgical limb
3. Compromised immune system based on medical history (e.g., immunosuppressive therapies such as chemotherapy, radiation, sepsis, infection), or other conditions that places the subject at increased risk of infection
4. Implanted spinal cord stimulator, cardiac pacemaker/defibrillator, deep brain stimulator, or other implantable neurostimulator whose stimulus current pathway may overlap
5. History of bleeding disorder
6. Antiplatelet or anticoagulation therapies other than aspirin
7. Allergy to skin-contact materials (occlusive dressings, bandages, tape etc.)
8. Incarceration
9. Pregnancy
10. Moderate pain (NRS > 3) in an anatomic location other than the surgical site
11. Anxiety disorder
12. History of substance misuse
13. Inability to communicate with the investigators
14. Inability to contact the investigators during the treatment period, and vice versa (e.g., lack of telephone access)
15. Allergy to amide local anesthetics
16. Morbid obesity (body mass index > 40 kg/m²)

5.3 LIFESTYLE CONSIDERATIONS

Not Applicable.

5.4 SCREEN FAILURES

Screen failures are defined as participants who consent to participate in the clinical trial but are not subsequently randomly assigned to the study intervention or entered in the study.

6 STUDY INTERVENTION

6.1 STUDY INTERVENTION(S) ADMINISTRATION

6.1.1 STUDY INTERVENTION DESCRIPTION

For individuals of childbearing potential, a sample of urine will be collected before any study interventions to confirm a non-pregnant state (this is standard procedure for all surgical patients) **[standard of care]**.

The RELAY device combines a catheter-over-needle to permit ultrasound-guided percutaneous insertion with the tip adjacent to a peripheral nerve or plexus, followed by needle removal which leaves the catheter in situ to deliver a bolus of local anesthetic (if desired) and subsequent perineural local anesthetic infusion (if desired). The catheter also has 3 integrated electrodes to enable neuromodulation using the integrated pulse generator and battery (figure below).

Participants will have standard external monitors placed and oxygen delivered by facemask or nasal cannula **[standard of care]**. The peripheral nerve block site(s) will be cleansed with chlorhexidine gluconate and isopropyl alcohol **[standard of care]**. Intravenous sedation/analgesia with midazolam and/or fentanyl will be titrated for patient comfort as is standard for peripheral nerve block administration **[standard of care]**. *The nerves treated will include the sciatic proximal to the popliteal crease for foot surgery and the brachial plexus for shoulder surgery* **[standard of care]**. The target nerve(s) will be visualized with ultrasound using a transverse cross-sectional (short axis) view and a skin wheal of local anesthetic will be raised inferior to the transducer to anesthetize the skin and then the track towards the target **[standard of care]**.

Treatment group allocation (randomization).

All participants in the training run-in period will receive active neuromodulation **[research specific]**.

Participants in the randomized portion of the study will be randomized and allocated to one of two possible treatments groups **[research specific]**:

- **Neuromodulation**
- **Sham (Control)**

Postoperative Day	0 [Day of surgery]	1	2	3	4	5	6	7	8	9	10	11	12	13	14
Neuromodulation	Electric current														
Control	No electric current														

Randomization [**all research specific**] will be stratified by anatomic location (shoulder and foot/ankle surgery) in a 1:1 ratio and in blocks of 2. Computer-generated randomization lists will be created by the UC San Diego Investigational Drug Service and the allocation provided to the investigators *via* sequential, opaque envelopes. Pulse generators are available that are capable of either (1) passing electrical current; or (2) not passing electrical current. Importantly, these 2 modes (active and sham) are indistinguishable in appearance, and therefore investigators, participants, and all clinical staff will be masked to treatment group assignment, with the only exception being the unmasked individuals who insert the RELAY and program the stimulator.

The RELAY system with the integrated needle will be inserted adjacent to the target nerve with an in-plane approach [**same as standard-of-care**]. Dextrose 5% in water (1-20 mL) will be injected via the needle to open a space around the target nerve(s) [**research specific**], the catheter advanced [**same as standard-of-care**], and the needle subsequently withdrawn [**same as standard-of-care**].

Electrical current will be introduced with increasing intensity via each of the anode electrodes to optimize participant's perceived stimulation (control provided by the Gate Keeper app from an investigator's phone or tablet). Accurate lead placement will be confirmed with subject reports of comfortable sensations over the surgical site without eliciting muscle contractions. The minimum threshold and maximum comfortable amplitudes will be determined along with the optimal frequency, pulse duration, and anode/cathode. Starting from the lowest possible current we increase the current until the participant states that they feel a "buzzing" sensation (some describe it as a "comfortable massage"). That is the minimal sensed current. We then continue increasing with the instructions to let us know when it starts to be less comfortable—and to stop us before it hurts. That is the maximum comfortable current. The stimulator will be then set to deliver the minimum threshold amplitude and turned off for surgery. **Sham treatment group [all research specific]**. For participants receiving **sham** treatment, electric current will not reach the anodes, but the investigators will connect to the RELAY to the mobile phone or tablet just as with the active group and set the parameters as follows: anode (distal), cathode (proximal), frequency (100 Hz), pulse duration (100 μ s), and amplitude (5 mA).

Local anesthetic for active and sham groups. Local anesthetic (10 mL of lidocaine 2% with epinephrine) will be injected with negative aspiration every 3 mL and resulting sensory block confirmed to ensure accurate catheter tip placement [**research specific**]. Following block confirmation (sensory deficits in the expected nerve distributions), the RELAY will be affixed with both surgical adhesive (2-Octyl 2-cyanoacrylate) at the entry site and a chlorohexidine-impregnated occlusive dressing [**research specific**]. Subsequently, 10 mL of bupivacaine 0.5% with epinephrine will be injected negative aspiration every 3 mL along with a supplemental single-injection saphenous nerve block for foot/ankle surgery [**standard of care**].

Intraoperatively, surgeons will be permitted to infiltrate the surgical area with long-acting local anesthetic as their common practice dictates [**standard of care**].

Postoperatively, the stimulators will be connected to participants' phones and turned on [**research specific**].

For the training run-in period, if a patient's surgeon requests a postoperative continuous peripheral nerve block, a ropivacaine 0.2% infusion will be provided per standard UC San Diego protocol [**standard of care**].

After 7 days, participants in both the active and sham groups, themselves or their caretaker will remove the occlusive dressing and withdraw the catheter (and integrated electrodes) with gentle traction and rotation at home [**research specific**]. The devices are single-use and disposable [**research specific**].

Following study completion, the results will be mailed electronically or by the United States Postal Service to all enrolled participants in written form using non-technical (e.g., “layperson”) language [research specific].

6.1.2 DOSING AND ADMINISTRATION

The pulse generator of the RELAY has a frequency between 1-250 Hz, a pulse duration of 1-200 μ s, and a current of 0.001-10 mA (1-10,000 μ A). We will maximize frequency, minimize pulse duration, and have participants adjust the amplitude, as needed. Administration is described above in 6.1.1.

6.2 PREPARATION/HANDLING/STORAGE/ACCOUNTABILITY

6.2.1 ACQUISITION AND ACCOUNTABILITY

The RELAY device will be shipped to the clinical trial site by Gate Science. Accountability records will be maintained at the site.

Any investigational medical device that is defective will be sent back to Gate Science, and the investigational medical device will be resupplied to replace the defective. When the device is explanted, it will be discarded. Any remaining device at the site at the end of the study will be returned to Gate Science.

6.2.2 FORMULATION, APPEARANCE, PACKAGING, AND LABELING

Not applicable to this trial involving the investigation of a medical device, as opposed to a medication.

6.2.3 PRODUCT STORAGE AND STABILITY

The RELAY system will be stored in the Principal Investigator’s or Program Manager’s locked office or the locked anesthesia workroom.

The expiration of RELAY is based on date of manufacture and is provided to the clinical trial site and will be monitored accordingly by the Sponsor.

6.2.4 PREPARATION

The RELAY devices do not need “preparation”.

6.3 MEASURES TO MINIMIZE BIAS: RANDOMIZATION AND BLINDING

The randomized portion of the study will utilize a randomized, observer- and participant-masked, sham/placebo-controlled protocol. Randomization will be stratified by surgical procedure (shoulder and foot/ankle surgery) in a 1:1 ratio and in blocks of 2. Computer-generated randomization lists will be created by the UC San Diego Investigational Drug Service and the allocation provided to the investigators in sequential, opaque envelopes. A masking assessment question will be queried on postoperative Day 1.

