	
Treatment group allocation (randomization). Participants in the training run-in period will all receive active neuromodulation. Participants in the randomized portion will be randomized (1:1) to one of two possible treatments groups:
 
○ Neuromodulation (Active)○ Sham (Control) 
Randomization will be stratified by anatomic location (shoulder and foot/ankle surgery) in a 1:1 ratio and in blocks of 2. Computer-generated randomization lists will be created by the UC San Diego Investigational Drug Service and the allocation provided to the investigators via sequential, opaque envelopes.
 
Pulse generators are available that are capable of either (1) passing electrical current; or (2) not passing electrical current. Importantly, these 2 modes (active and sham) are indistinguishable in appearance, and therefore investigators, participants, and all clinical staff will be masked to treatment group assignment, with the only exception being the unmasked individuals who insert the RELAY and program the stimulator.
 
The RELAY system with the integrated needle will be inserted adjacent to the target nerve with an in-plane approach. Dextrose 5% in water (1-20 mL) will be injected via the needle to open a space around the target nerve(s), the catheter advanced, and the needle subsequently withdrawn.
 
Active (neuromodulation) group. For participants receiving active (neuromodulation) treatment, electrical current will be introduced with increasing intensity via each of the anode electrodes to optimize participant's perceived stimulation (control provided by the Gate Keeper app from an investigator's phone or tablet). Accurate lead placement will be confirmed with subject reports of comfortable sensations over the surgical site without eliciting muscle contractions. The minimum threshold and maximum comfortable amplitudes will be determined along with the optimal frequency, pulse duration, and anode/cathode. Starting from the lowest possible current the current will be increased until a participant states that they feel a "buzzing" sensation (some describe it as a "comfortable massage"). That is the minimal sensed current. The current will then continue to be increased with instruction to the participant to let the investigator know when it starts to be less comfortable—and to stop the investigator before it hurts. That is the maximum comfortable current. The stimulator will then be set to deliver the minimum threshold amplitude and turned off for surgery.
 
Sham (control) group. For participants receiving sham treatment, electric current will not reach the anodes, but the investigators will connect the RELAY to the Gate Keeper app just as with the active group and set the parameters as follows: anode (distal), cathode (proximal), frequency (100 Hz), pulse duration (100 μs), and amplitude (5 mA).
 
Local anesthetic for active and sham groups. Local anesthetic (10 mL of lidocaine 2% with epinephrine) will be injected with negative aspiration every 3 mL and resulting sensory block confirmed to ensure accurate catheter tip placement. Following block confirmation (sensory deficits in the expected nerve distributions), the RELAY system will be affixed with both surgical adhesive (2-Octyl 2-cyanoacrylate) at the entry site and a chlorohexidine-impregnated occlusive dressing. Subsequently, 10 mL of bupivacaine 0.5% with epinephrine will be injected negative aspiration every 3 mL

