9.4 STATISTICAL ANALYSES

9.4.1 GENERAL APPROACH

Baseline characteristics of the randomized groups will be summarized with means, standard deviations, and quartiles. Balance between groups will be assessed following the approach described by Schober (2018). Specifically, standardized differences will be calculated using Cohen's d whereby the difference in means or proportions is divided by the pooled standard deviation estimates. Any key variables (age, sex, height, weight, BMI, and surgical procedure) with an absolute standardized difference greater than $1.96 \times \sqrt{2/n} = 0.716$, where $n = 15$ is the target sample size per group (Austin (2009)), will be noted and included in a sensitivity analysis with a generalized linear model (e.g. linear regression for pain severity NRS or logistic regression for incidence rates) to obtain an estimate of the treatment effect adjusted for the imbalanced covariate(s). If key model assumptions are violated (i.e. homoscedasticity or Gaussian distribution for linear models), data transformations and/or alternative generalized linear models will be applied as appropriate. Missing data is expected to be negligible. In the event of unexpected missing data, multiple imputation by chained equations (Stef van Buuren, Karin Groothuis-Oudshoorn (2011). mice: Multivariate Imputation by Chained Equations in R. *Journal of Statistical Software*, 45(3), 1-67) will be applied to obtain estimates of treatment effects under the assumption of missing at random. The imputation model will exhaustively consider all measured baseline covariates and longitudinal observations to maximize the likelihood that the missing at random assumption is met.

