10 SUPPORTING DOCUMENTATION AND OPERATIONAL CONSIDERATIONS

10.1 REGULATORY, ETHICAL, AND STUDY OVERSIGHT CONSIDERATIONS

10.1.1 INFORMED CONSENT PROCESS

Enrollment. Potential study participants will be identified from the surgical schedule:

Candidates who meet inclusion and exclusion criteria and desire study enrollment will be scheduled to arrive the day of surgery 30 to 60 minutes earlier than normal to allow for written informed consent, baseline information collection, and additional time for study procedures. Written informed consent will be attained prior to any measurements or procedures prior to surgery. When participants present for surgery, an investigator, Program Manager, or research coordinator will provide and attain written informed consent. This will occur in private patient care areas, so that participants may feel comfortable asking questions.

We do not foresee any issues relevant to the mental capacity of the potential human participants. Written, informed consent will be attained prior to any study procedures or measurements; and participants will not receive procedure-related sedation until following the written, informed consent process is completed. Participants will be provided privacy and time for decision making both in the study description/explanation telephone call by an investigator as well as the morning of surgery using a private patient care area to again review the study, informed consent form, and answer any remaining questions. As noted previously, participants may speak with an investigator by telephone from initial contact through the morning of treatment; and will have access during and following the treatment(s) with cellular phone and pager numbers provided upon discharge.

This study protocol has follow-up data-collection telephone calls a maximum of 14 days following the initial study treatment, so repeated informed consent following the initial consent is unnecessary, as opposed to multi-year, longer-term clinical trials. Surrogate consent will not be accepted; therefore, if human participants cannot provide consent on their own, they will not be offered study enrollment. Consent by an individual's Legally Authorized Representative is unacceptable for study enrollment.

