Following informed consent and the signing of the UCSD IRB-approved ICF and HIPAA documents, these documents will be copied, and the copy placed in the patient's medical record. The participant will be provided a copy along with the Participants' Bill of Rights.

We are requesting a partial waiver of HIPAA authorization for recruitment as protected health information will be reviewed to ascertain appropriate inclusion/exclusion criteria:

The investigators will need to know in advance which participants would like to participate in order to have an investigator and research coordinator present on the day of surgery. The investigators therefore need to contact potential participants prior to their day of surgery and request a waiver of consent for recruitment purposes. We will scan the upcoming surgery schedule (which we have access to being anesthesiologists—we use this schedule daily for medical purposes), identify participants having the types of surgical procedures specified for this study, look in their electronic records to determine eligibility, and if eligible either call the potential participants ourselves or provide the name and contact information to a research coordinator to contact the potential participants.

1. These procedures are minimal risk to the potential participants as we are anesthesiologists who will be viewing these records even without study participation in preparation for surgery and postoperative analgesia planning. There is no information that an anesthesiologist would not view regardless of the existence of the study.

2. A waiver of consent would not adversely affect the rights and welfare of the potential participants as we are anesthesiologists who will be viewing these records even without study participation in preparation for surgery and postoperative analgesia planning. There is no information that an anesthesiologist would not view regardless of the existence of the study.

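### Fixed blocks of 2, disclosed in the protocol, let unmasked staff deduce up to half of the allocations before the participant is enrolled

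*Combined protocol and SAP*

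**What the plan says.** The block size appears in three places. Section 6.3 reads "Randomization will be stratified by surgical procedure (shoulder and foot/ankle surgery) in a 1:1 ratio and in blocks of 2", and the Synopsis (1.1) reads "Randomization will be stratified by anatomic location (shoulder and foot/ankle surgery) in a 1:1 ratio and in blocks of 2". Section 6.1.1 repeats "stratified by anatomic location (shoulder and foot/ankle surgery) in a 1:1 ratio and in blocks of 2". The available text mentions no varied or withheld block size. The Investigational Drug Service creates the lists, and the allocations reach the investigators in opaque envelopes used in order.

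Masking covers investigators, participants and clinical staff, "with the only exception being the unmasked individuals who insert the RELAY and program the stimulator" (6.1.1). The trial has one center.

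On recruitment, section 10.1.1 has the anesthesiologist investigators scan the surgical schedule, "look in their electronic records to determine eligibility, and if eligible either call the potential participants ourselves", or hand the contact to a research coordinator. On the day of surgery, "an investigator, Program Manager, or research coordinator will provide and attain written informed consent". The available text does not bar those who insert or program the device from screening, calling or consenting, and does not say when the envelope is opened relative to consent. The bodies of sections 10.1.5 (Key Roles and Study Governance) and 10.2.5 (research team responsibilities) were not in the copy reviewed, so a separation of roles could be set out there.

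**The concern.** Concealment means that whoever decides on the next participant cannot know the next allocation. With a known block size of 2, that fails for every second slot. The usual safeguards do not help:

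- Opaque envelopes do not help, because the deduction comes from the previous case.
- Stratification does not help, because the schedule shows whether the next candidate is a shoulder or a foot/ankle case.

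Someone who knows the next allocation can let it influence whom to approach, or when. The primary endpoint is self-reported pain in about 40 participants. Masked participants and outcome assessors do not protect against this, because selection acts before treatment.

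The planned covariate adjustment would repair it only in part. Section 9.4.1 says: "Any key variables (age, sex, height, weight, BMI, and surgical procedure) with an absolute standardized difference greater than" 0.716 are carried into an adjusted model. Expected pain, sub-diagnostic anxiety or motivation are not on that list, and smaller imbalances in the listed variables trigger nothing.

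**Working it through.** **The plan's own figures.** The documents give no figure for predictability of allocation. The related design figure is 85.2% power in section 9.2 (20 per group, SD 2.05, difference 2 points). A two-sample t-test at two-sided 0.05 reproduces it: 85.2%. This point does not change the power; the 2-point difference serves below only as a yardstick.

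**Inputs.** Block size 2, ratio 1:1 and two strata (6.3); 40 randomized, up to 50 (9.3). The number of operators is inferred from the run-in in section 4.1: up to 20 participants at about "5 to 10 catheter lead insertions per anesthesiologist" gives 20/10 = 2 to 20/5 = 4. It is not stated for the randomized part.

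**Blocks of 2, all earlier allocations known.**
- Certain share: 1 slot of every 2, so 20 of 40 (19 if both strata end on an odd count), or 25 of 50 (24 if both are odd).
- Best-guess rate: 0.5 × 1 + 0.5 × 0.5 = 75%, against 50% by chance. That is 40 × 0.25 = 10 extra correct guesses.

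**Operators who share nothing.** With cases falling at random among k operators, the operator doing the second case of a pair did the first with probability 1/k. Certain share = 0.5/k; best guess = 0.5 + 0.5 × share.

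| k | Certain share | Allocations of 40 | Best guess |
|---|---|---|---|
| 1, or full sharing | 50% | 20 | 75% |
| 2 | 25% | 10 | 62.5% |
| 3 | 16.7% | 6.7 | 58.3% |
| 4 | 12.5% | 5 | 56.3% |

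**Alternatives.** The guesser is assumed to know every earlier allocation in the stratum and the set of possible sizes, taken as equally likely, but not their order. Fixed blocks are enumerated exactly. Mixed blocks are simulated (20,000 lists per stratum size). Twenty per stratum is an assumption; 19 and 21 show odd sizes.

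| Scheme, stratum size | Certain | Best guess | Mean imbalance | Maximum imbalance |
|---|---|---|---|---|
| Fixed 2, n = 20 | 50% | 75% | 0 | 0 |
| Fixed 2, n = 19 | 47.4% | 73.7% | 1 | 1 |
| Fixed 4, n = 20 | 33.3% | 70.8% | 0 | 0 |
| Mixed 2/4/6, n = 20 | 3.7% | 69.7% | 0.37 | 2 |
| Mixed 2/4/6, n = 19 | 3.7% | 69.0% | 1.04 | 3 |
| Mixed 2/4/6, n = 21 | 3.7% | 69.1% | 1.03 | 3 |

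Over both strata the mixed scheme can reach 2 + 2 = 4 at even sizes or 3 + 3 = 6 at odd sizes. In simulation, a total imbalance of 4 or more occurred in about 2% of lists, both at 40 participants and at the 20-participant futility look.

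**Worst-case illustration (assumption only).** Let f be the share of each arm that is known. Suppose every known active slot is steered d points down and every known sham slot d points up, a gap of 2d between steered slots. Each arm mean moves f × d, so the bias is 2 × f × d. With d = 0.5:
- f = 0.5: 2 × 0.5 × 0.5 = 0.5 point, a quarter of the 2-point target.
- f = 0.25: 0.25 point.
- f = 0.125: 0.125 point.

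Steering only the active slots halves each figure.

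**The case against.** The strongest reply is that the route from knowledge to bias is permitted but not documented. Nothing says that those who insert or program also recruit. A coordinator may make the calls, the Program Manager or a coordinator may take consent, and the unavailable role sections could separate the tasks. This stands as a limit: the point is a vulnerability that the available text leaves open, and it does not show misuse.

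Second, 50% requires every first-of-pair allocation to be known. Operators who share nothing reach only 12.5% to 25%. This also stands; 50% is an upper bound.

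Third, candidates come from an existing schedule and are called before surgery, while randomization is on Day 0. A candidate's slot is certain only after the preceding same-stratum case has been randomized, which can leave little more than the morning of surgery in which to act. This narrows the opportunity without closing it, because eligibility and consent are still settled that morning.

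Fourth, varied blocks lower the best-guess rate only from 75% to about 70%. That is correct; the gain lies in certainty, which falls from 50% to about 4%. The size of the bias illustration has no basis in the documents and should not be read as an estimate.

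**Conclusion.** The concern holds. Up to 20 of 40 allocations (50%) can be known with certainty before enrolment if earlier allocations are known or shared, and 12.5% to 25% if 2 to 4 operators keep strictly to their own cases. The block size, its disclosure and the unmasked role are stated outright. Three things rest on inference or assumption: the number of operators, the overlap between unmasked staff and recruiters, and any size of bias. It is a design weakness that should be corrected because correction is cheap. It does not show that the results would be biased.

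**What to change.** Have the Investigational Drug Service generate permuted blocks of randomly varying size, for example 2, 4 and 6, within each stratum. Remove the block size from the Synopsis and from sections 6.1.1 and 6.3, and keep it in a document that only that service holds. If randomization has begun, apply the new list to the remaining allocations.

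The work is one regenerated list and one sentence edited in three places. The downside is a final imbalance per stratum of at most 2 at even sizes (mean 0.37 at 20) and at most 3 at odd sizes (mean about 1.03 at 19 or 21), against 0 and 1 with blocks of 2.

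Because the best-guess rate falls only modestly, a useful addition is to state that unmasked staff take no part in screening or consent, and that each envelope is opened only after consent and enrolment. If the role sections already say so, a cross-reference in section 6.3 is enough.
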